
Aim 2: Cost. With N=131 available per arm (N=262 total) and α =0.05 we have 80% power to detect differences in mean cost per participant of 0.35 SDs. For example, if the SD for cost is \$100, then we have 80% power to detect differences in mean cost per participant of \$35.

Aim 3: Predictors (exploratory). With N=131 available per arm (N=262 total) and α =0.05 for continuous predictors we have 80% power to detect correlations of 0.243 with 12-month percent weight loss. With N=131 available per arm (N=262 total) and setting α =0.05, for categorical variables, detectable differences in mean percent weight loss depend on the proportion of the predictor in the sample. For a predictor with 50% prevalence (i.e., n=65 and n=66 with vs without the characteristic), we have 80% power to detect differences of 0.49 SDs. For predictors with 33% prevalence, we can detect differences of 0.52 SDs. For predictors with 20% prevalence, 0.62 SDs, and for predictors with 10% prevalence (i.e., n=13 vs n=118), 0.82 SDs. For estimated SD=5.5% for 12-month percent weight loss, this indicates differences of 2.7%, 2.9%, 3.4%, and 4.5% weight loss, respectively. Sample size calculations for Aims 2 and 3 were conducted using Stata.

For EACH Participant Population State Describe the Study Population(s): [Describe the participant population(s) including gender, ethnicity, income, level of education and age range.]

We will be recruiting from a representative population of individuals that live or work around Worcester MA and Storrs CT. We are recruiting men and women of all ethnicities, income and education levels between the ages of 18 and 65. Thus far we have had less success recruiting minorities and men and have put additional effort towards that goal. We will recruit participants in 9 waves off set by 2-3 months each. Waves 1-6 were recruited and carried out at UMass and waves 7-9 will be recruited and carried out at UConn.

We will also collect intervention delivery and feedback data from the interventionists. Interventionists are trained in the delivery of the DPP and are set up as consultants.

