Participants will complete a telephone screening, an in-person baseline, and an online webinar (described above). Eligible participants will then be randomized to one of two 12-month weight loss interventions: online (Get Social) or in-person (Traditional). Follow-up assessments will occur at 6- and 12-months.

Randomization: Randomization will take place after the baseline procedures are complete once we've determined eligibility. Participants will be randomized to the Get Social or the Traditional condition. We will randomize 36-40 participants for each recruitment wave, for a goal of approximately 18 per condition. Participants will be randomized 1:1 to the two study conditions in randomly permuted blocks of size 4 and 6 using the ralloc program in Stata Randomization and will be stratified by gender (male vs. female) and baseline BMI (27.0-34.9 vs. 35.0-45.0). The randomization list was generated at the start of the study before randomization. The list is managed by the program director. Once a participant has been determined to be eligible, the program director will assign each participant to the next open assignment on the list. The program director will then tell the research assistant who will reach out to participants to inform them via e-mail of the condition assignment.

Orientation-Visits:

- Traditional participants: This in-person group will last 1 hour and will include training on The first session of the intervention will be extended from 1.5 hours to 2 hours in order to provide time for the orientation which will cover: -My Fitness Pal, an overview of their participation, and study goals. My Fitness Pal is an app that can be used to track diet and physical activity. It can be used on a computer or mobile app. Participants will receive their study goals for weight loss (1-2 lbs. per week), diet, and physical activity. The weight loss goal is approximately 7% weight loss over a 12 month period. This orientation may be completed on an individual in-person basis or phone for people unable to attend the group, though this option won't be encouraged. The weight loss goal is provided in the My Fitness Pal app. –The orientation group is led by the interventionist, a post-doctoral fellow, and a research assistant. and research assistants.

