- Traditional participants will receive the DPP intervention during in-person group visits. Groups will include 18 participants each. During the first 6 months, groups will be held weekly for 8 weeks, then biweekly for 16 weeks. Groups will be held monthly between 6- and 12-months. There will be a total of 22 groups and each group will last 90 minutes (except for the first group which will be extended to 2 hours to accommodate the orientation) and each one will be audio recorded to track intervention-adherence. Participants will have weight taken in-person before the start of each group. During the weeks participants do not have a group, they will be encouraged to take their weight at home and e-mail it to study staff. Staff will e-mail them during these weeks asking for their current weight. The e-mail text wording is included in the measures attachment.
- Get Social participants will receive the DPP intervention in a "protected" Twitter group. Where participants and counselors will activate the "protected tweets" privacy setting so that the tweets are only viewable to each other. The DPP content has been restructured to deliver in an online context. The delivery includes a morning and evening post each day. The online coaches will log in twice daily to respond to questions, address concerns, and encourage engagement. Participants will receive an e-mail asking for their current weight, the minutes per week they used Twitter, and questions about treatment receipt. These e-mails will be sent during the same weeks that the Traditional participants have a group. The questions for this survey will all appear together accessible by one link. See measures attachment for survey. When reporting time on Twitter, participants will Androids will be asked to download an app called App Usage Tracker. This app is free and downloaded from the Play Store and tracks time spent on apps.
- Interventionists will be asked at to complete a survey at the 6 month timepoint. The survey link will be emailed at the 6 month time point in each wave. The survey will ask about their experience delivering the intervention. If they do not respond we will follow up with them via email or phone. Once they have delivered interventions to participants in both the Get Social and Traditional conditions the survey will also ask for their opinions comparing and contrasting their preferences for each condition.

Follow up:

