2/26/2021

Statistical Analysis Plan

Study Title: Get Social: Randomized Trial of a Social Network Delivered Lifestyle Intervention

NCT02646618

Preliminary analysis

Baseline participant characteristics will be examined by condition. If groups differ on certain characteristics, these variables will be included as covariates in the primary analyses. Other preliminary analyses include assessing patterns of missing data, dropout rates, distributional properties of dependent measures, and correlations among outcome measures. A series of sensitivity analyses will be performed to examine the extent of potential bias by assuming the participants who dropped out are (i) missing completely at random (i.e., independent of the outcome), (ii) are responders to the intervention, or (iii) are non-responders to the intervention. Multiple imputation and other methods will be explore to address missing data for variables for which more than 5% of data are missing.

Primary non-inferiority outcome

We will model percent weight loss at 12 months using a linear mixed model, with percent weight loss as the dependent variable and study condition as the independent variable and accounting for repeated measures of weight. Test of the intervention condition indicator will provide a statistical test of the intervention effect and the estimated coefficient, along with the estimated confidence interval. This analytic approach aims to test whether the Get Social condition is not appreciably worse than (i.e., not inferior to) the traditional condition for percent weight loss at 12 months by our a priori inferiority margin of 2%. The effect estimates will reveal clinical non-inferiority of the Get Social condition if the confidence interval lies completely above $-\Delta$ or clinical non-inferiority of the traditional condition if the confidence interval lies completely below $+\Delta$, i.e., 2%.

Secondary non-inferiority outcomes

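### The primary model has no term for recruitment wave or institution; naming wave in advance would modestly narrow the deciding interval if waves differ by more than about 0.6-0.7 points SD

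*SAP*

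**What the plan says.** Protocol, study population: "We will recruit participants in 9 waves off set by 2-3 months each". On place: "Waves 1-6 were recruited and carried out at UMass and waves 7-9 will be recruited and carried out at UConn".

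Protocol, Randomization: "We will randomize 36-40 participants for each recruitment wave, for a goal of approximately 18 per condition". On method: "Participants will be randomized 1:1 to the two study conditions in randomly permuted blocks of size 4 and 6". The allocation "will be stratified by gender (male vs. female) and baseline BMI (27.0-34.9 vs. 35.0-45.0"); wave and site are not strata. The list was generated once, at the start, and each eligible participant takes the next open place.

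Protocol, Intervention Phase, on the in-person arm: "Groups will include 18 participants each". With about 18 per condition in a wave, each wave holds roughly one treatment group per arm.

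SAP, Primary non-inferiority outcome: the mixed model is specified "with percent weight loss as the dependent variable and study condition as the independent variable and accounting for repeated measures of weight". The protocol's Data Analysis section has a linear regression on condition. Neither names wave or site.

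SAP, Preliminary analysis, on covariates: "If groups differ on certain characteristics, these variables will be included as covariates in the primary analyses".

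Protocol, Justification of Sample Size: intraclass correlation within treatment groups was considered and set aside, citing earlier research that found no clustering. Variation between waves or institutions is not discussed.

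**The concern.** Both arms of a wave share a recruitment period, an institution and a local population, and the institution changes after wave 6. If mean weight loss varies by wave, the model counts that variation as error in the arm comparison, although small 1:1 blocks keep the arms nearly balanced within a wave. The reported standard error is then larger than the real sampling variation.

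The covariate rule does not fill the gap. It selects on imbalance between arms, whereas precision comes from adjusting for factors that predict outcome, balanced or not.

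At stake is a little width on the interval that decides non-inferiority. Separately, no planned output shows whether the arm difference looks similar at the two institutions, although a third of the waves run at the second.

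**Working it through.** **1. The plan's own figure.** Inputs from the protocol's sample size section: margin 2, SD 5.5, alpha 0.05, power 90%, true difference 0.

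- Normal formula, one-sided 0.05: n = 2 × (1.645 + 1.282)² × 5.5² / 2² = 130 per arm. The t-based version gives 131, as stated, with power 90.2%.
- 131 / 0.8 = 163.75, so 164 per arm and 328 in total, as stated.
- One-sided 0.025 gives 159 (t-based 160) and does not reproduce. The interval level is not stated; 90% two-sided is assumed below because it matches the stated N.

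**2. Interval without a wave term.** SE = 5.5 × √(2/131) = 0.680. Half-width = 1.651 × 0.680 = 1.122 points.

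**3. With a wave term, under perfect balance.** Let ρ be the share of total variance common to both arms of a wave. The residual SD is 5.5 × √(1 − ρ), on 252 instead of 260 degrees of freedom. No document gives ρ, so a range including zero is shown.

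| ρ (assumed) | Wave SD | Half-width | Power |
|---|---|---|---|
| 0 | 0 | 1.122 | 90.2% |
| 0.01 | 0.55 | 1.116 | 90.4% |
| 0.02 | 0.78 | 1.111 | 90.7% |
| 0.05 | 1.23 | 1.094 | 91.4% |
| 0.10 | 1.74 | 1.064 | 92.6% |

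**4. With realistic imbalance.** Blocks run on across waves, so balance within a wave is only approximate. Trials were simulated with 328 participants in nine waves, stratified blocks of 4 and 6, 20% random dropout and a single 12-month outcome. The interval width with wave, relative to without, was 1.006, 1.001, 0.997, 0.983 and 0.960 at the five values of ρ. Break-even is near ρ = 0.013, and 5.5 × √0.013 = 0.63 points.

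The same comparison by wave SD:

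| Wave SD (assumed) | SE without | SE with | Change |
|---|---|---|---|
| 0 | 0.678 | 0.682 | +0.6% |
| 1 | 0.676 | 0.671 | −0.7% |
| 1.5 | 0.677 | 0.657 | −3.0% |
| 2 | 0.675 | 0.637 | −5.6% |

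Simulated power gains at 1, 1.5 and 2 are about 0, 1.3 and 1.6 points. At SD 0, power falls slightly (90.4% to 90.2%). As an equivalent number of participants, 262 × [(SE without / SE with)² − 1] gives about 4, 16 and 32 of 262.

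**5. What adjustment changes.** At wave SD 1.5, simulation put the actual SD of the unadjusted difference at 0.651, its reported SE at 0.676 and the adjusted SE at 0.656. Blocking already delivers most of the precision; the wave term mainly brings the reported SE into line.

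**6. Variation specific to one arm's group.** There are 262 / 18 = 14.6 evaluable participants per group. At an assumed group ICC of 0.02 the variance inflation is 1 + 13.6 × 0.02 = 1.27, so the true SE is √1.27 = 1.13 times the reported one. A nominal 90% interval then covers 2Φ(1.645/1.13) − 1, about 86%, with one-sided error about 7%. Simulation gives about 85-86% coverage with or without a wave term. Under balance, the net interval is too wide only if wave variance exceeds about 13.6 times group variance.

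**7. By institution** (equal waves, 20% dropout). UConn: 3 × 262 / 9 = 87 evaluable, with 90% half-width 1.663 × 5.5 × √(4/87) = about 1.96 points.

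**The case against.** The strongest case against is that the gain rests on a quantity the documents do not supply. Their one relevant statement, that weight loss does not cluster within treatment groups, points to a low value, because shared wave variance is part of the correlation within a group. This stands, and it is why the point is conditional. It does not settle the matter: the protocol's reasoning there concerns social influence among group members, not a change of institution or population.

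Some sources of wave variation are also weak. Outcome is change over 12 months, so baseline and endpoint fall at the same time of year and season should matter little. The protocol mentions balancing conditions across coaches but does not say that both arms of a wave share a coach. If they do not, coach variation is arm-specific and a wave term cannot remove it. Both observations stand.

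A reader might infer that the planned interval is definitely too wide, or that the reported SE is too large. The documents do not support this: with no shared variance a wave term slightly widens the interval, and with any appreciable group-specific variance the planned interval is too narrow. Nor should a reader infer that adjusting for wave deals with clustering. It leaves that error in place and can narrow an interval that is already too narrow, the riskier direction in a non-inferiority trial.

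The check by institution would be imprecise: the UConn half-width is about the whole 2-point margin. That limits it to description.

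**Conclusion.** The point holds as a modest, conditional improvement. Wave and institution are absent from the primary model and nothing else in the plan would bring them in. If between-wave SD exceeds about 0.6-0.7 points, the SE is larger than needed by about 0.7%, 3% or 6% at 1, 1.5 or 2 points, worth roughly 0 to 1.5 points of power. Below that there is nothing to gain.

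These figures rest on assumed wave variances, a 90% interval, random dropout and a simulation of the 12-month outcome alone rather than the full repeated-measures model. The omission introduces no bias. It does not undermine the planned N, because the 5.5% is a total SD.

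**What to change.** In the SAP's primary model, add recruitment wave as a fixed effect with nine levels. Site is nested in wave, so no separate site term is needed. Report the 12-month arm difference with its confidence interval for UMass (waves 1-6) and UConn (waves 7-9), labelled descriptive, with no claim of non-inferiority at either institution.

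Add a sensitivity analysis with a random effect for treatment group, since the wave term does not cover variation specific to one arm's group.

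The cost is SAP wording, 8 degrees of freedom out of about 260, and an interval about 0.6% wider if waves do not differ. No new data are needed: wave is fixed at entry and known for everyone. If the change is made after outcome data have been seen, label it so.

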Aim 1: Efficacy. Our sample size estimates utilize methods developed specifically for non-inferiority trials.72 In a non-inferiority trial, the null hypothesis (H0) is that the new treatment is inferior to the standard treatment, and the alternative hypothesis (HA) is that the new treatment is not inferior to the standard treatment. "Not inferior to" is defined by the non-inferiority margin, δ . Here, we set $\delta = 2\%$, based on a clinically meaningful difference in average weight loss between the two treatment arms. This means that if the Get Social condition loses up to 2% less weight on average than the Traditional condition, we will consider the Get Social condition to be non-inferior to the Traditional condition. If the Get Social condition loses >2% less weight then it will be considered inferior to the Traditional condition. Thus, adequate power for clinical non-inferiority requires a sample size such that there is better than 90% probability that the lower limit of the confidence interval lies above $-\delta$, if the true effect size is zero or above. We estimated SD=5.5% based on our previous, fully powered randomized trial.28 With alpha=0.05, and δ =2%, we have 90% power to conclude that the Get Social condition is not inferior to the Traditional condition with 131 participants per arm. Accounting for 20% attrition, we will enroll 328 participants total (164 per arm). We considered adjusting the sample for intraclass correlation but previous research shows that weight loss does not cluster among members of weight loss treatment groups.1 We do not believe that the social influence in online groups will be stronger in the Get Social condition. Studies of social influence suggest that team-based activities or recruiting relatives or friends can lead to weight loss clustering but we will not be using such an approach.1 That said, we do believe that after the intervention, peer-to-peer engagement may continue for longer because participants will continue to have a channel by which to communicate with one another. They will also have the opportunity to collect additional social ties outside of the intervention which may be the source of social support, but this is likely to vary greatly across participants (not within treatment groups) and we do not have evidence that such ties will exert social influence of the magnitude of team-based activities and closer ties (i.e., relatives, friends). Secondary outcomes. For the secondary outcomes, we calculated the non-inferiority margins so that we have 90% power to detect given N=131 per arm, setting α=0.05, and using observed SDs from the literature. For change in kcal/day energy intake at 12 and 18 months, we have 90% to detect that Get Social is not inferior to the Traditional condition with a non-inferiority margin of 182 kcal/day with SD=500 kcal/day.28,56 For change in moderate-to-vigorous intensity physical activity minutes per day at 6 and 12 months, the non-inferiority margin is 9.2 minutes/day with SD=25 minutes/day. For percent weight loss at 12 months, the non-inferiority margin is 2.2% with SD=5.5%.28 If weight losses are more variable at 12 mos than 6 mos, the detectable non-inferiority margin is 3.0% with SD=8.0%.57 Power calculations were conducted using PROC POWER in SAS.73,74

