For EACH Participant Population Describe Screening Procedures, if applicable: [Describe when participants will be screened and how this will occur. Include copies of all screening forms and related documents. Describe procedures to notify participants of the screening result. Tip: if screening will be conducted online or by phone prior to consent, be sure to request a waiver of signed consent, if appropriate. Provide a copy of the screening instrument.]

Telephone screening:

Interested participants will either call the study office or be called after sending an email expressing interest in the study in order to complete an initial telephone screening call, which will provide details about participating and an initial eligibility assessment. Eligible participants will be invited to a 90-minute baseline visit. Ineligible participants will be notified of their ineligibility at this time as well. Eligible participants will receive an e-mail after the call to confirm the baseline visit date/time. We are requesting a waiver of consent to perform this telephone screening. After the call, participants will be emailed a consent form to review before attending the inperson baseline visit.

Baseline Visit:

Participants will receive a reminder e-mail 1 day before their visit. This visit will last 90 minutes and will include the consent process, weight/height measurement, blood pressure reading, binge eating disorder interview, surveys, three 24-hour diet recall interviews, and PCP approval. During this visit, study staff will also review a randomization agreement with the participant. This agreement will outline the differences of the two conditions and the importance of enrolling participants who are ok with being in both. We will ask the participant to complete the checklist and sign the document. We will also ask condition-specific questions in the baseline survey to allow participants to express concerns about either condition.

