Participants will complete follow-up visits at 6- and 12-months. The visit will last 1 hour and will include a weight measurement, blood pressure reading, three 24-hour diet recall interviews, and repeated baseline measures. The online survey containing the measures will be e-mailed to participants 1 week prior to the scheduled follow-up visits.

Time Commitment:

Visit	GS Condition	TC Condition
	(in minutes)	(in minutes)
Telephone Screening (20 min)	20	20
Baseline (210 min total)	210	210
Visit (90 min)		
2 at-home dietary recalls (60 min)		
Online survey (60 min)		
Webinar (60 min)	60	60
Orientations	180	

GS: individual orientation (60 min)		
GS: group orientation (120 min)		
TC: group orientation (60 min)		
Intervention	750	1980
GS: approx. 35 min/week 8 weeks, 14 min/week		
for 16 weeks, 8 min/week for 28 weeks (12.5 hrs)		
TC: 22 1.5 hr groups (33 hrs)		
6-month (150 min total)	150	150
Visit (30 min)		
2 at-home dietary recalls (60 min)		
Online survey (60 min)		
12-month (150 min total)	150	150
Visit (30 min)		
2 at-home dietary recalls (60 min)		
Online survey (60 min)		
Total	1520 minutes	2630
	(approx. 25 hrs)	2570 minutes
		(approx. 434
		hrs)

Interventionist data collection:

The interventionists provide the following information, some of which will be used in the analysis:

- Weekly timesheets for invoicing their time (these hours are used to calculate time/cost needed to deliver the intervention aim 2).
- A 10 minute survey at the end of each 6-month phase for each wave used to gather interventionist feedback.

Measures

Data Collected	List of Measures	Baseline	During	6	12	Method
			Intervention	Months	Months	
BMI	Height	Х				REDCap
	Weight	Х	X (weekly)	Х	Х	REDCap
Medications	Brief Medication Questionnaire ¹⁰	Х		Х	X	REDCap
Blood pressure	Blood Pressure	Х		Х	Х	REDCap
Demographics	Income, employment, marital status, race/ethnicity, household composition*	Х				REDCap
Medical History	Assesses exclusionary medical conditions*	Х				REDCap
Personality factors neuroticism/ openness	Ten-Item Personality Inventory (TIPI) ¹¹	Х				REDCap
Binge Eating Disorder	SCID Interview ¹² for BED	Х				Interview
Physical Activity	Arizona Physical Activity Questionnaire ¹³	Х		Х	X	REDCap
Sleep Quality	STOP ¹⁴	Х		Х	Х	REDCap
	Insomnia Severity Index ¹⁵	X		X	X	REDCap
	Pittsburgh Sleep Quality Index Questions ¹⁶	Х		Х	X	REDCap

	History of sleep apnea diagnosis*	X		X	X	REDCap
	Previous or current treatment for sleep apnea*	X		X	X	REDCap
Depression	BDI ¹⁷	Х		Х	X	REDCap

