Chronic Pain	Brief Pain Inventory ¹⁸	Х		X	Х	REDCap
Quality of Life	EQ-5D-3L ¹⁹	X		X	Х	REDCap
Contamination	Weight-loss related social media use*	X			X	REDCap
Social media use	Social Media Use*	Х		Х	Х	REDCap
Dietary recall	3 24hr recalls (ASA24- Automated Self- Administered) ²⁰	X (3)		X (3)	X (3)	Online
Social support for weight management	WMSI ²¹	X		X	X	REDCap
Measure time spent on Twitter	Phone or app tracking		X			REDCap
Group engagement on Twitter	Engagement in group		X	X	X	Twitter
Treatment receipt	Questions each week related to intervention*		X			REDCap
Intervention acceptability and burden	Questions given at 6m follow-up* and time spent data extraction from getsocial.com			X	X	REDCap
Interventionist Feedback (Interventionists only)	Interventionist Survey*			X		REDCap

* Investigator-derived items

Data Analysis: [For all studies, specify the analytic techniques the researcher will use to answer the study questions. Indicate the statistical procedures (e.g. specific descriptive or inferential tests) that will be used and why the procedures are appropriate. For qualitative data, specify the proposed analytic approaches.]

Preliminary analysis

Baseline participant characteristics will be examined by condition. If groups differ on certain characteristics, these variables will be included as covariates in the primary analyses. Other preliminary analyses include assessing patterns of missing data, dropout rates, distributional properties of dependent measures, and correlations among outcome measures. A series of sensitivity analyses will be performed to examine the extent of potential bias by assuming the participants who dropped out are (i) missing completely at random (i.e., independent of the outcome), (ii) are responders to the intervention, or (iii) are non-responders to the intervention. Multiple imputation to impute missing data will be used if more than 5% of data are missing.

Primary non-inferiority outcome

We will model percent weight loss at 12 months using a linear regression model framework, with percent weight loss as the dependent variable and study condition as the independent variable. Test of the intervention condition indicator will provide a statistical test of the intervention effect and the estimated coefficient, along with the

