estimated confidence interval. This analytic approach aims to test whether the Get Social condition is not appreciably worse than (i.e., not inferior to) the traditional condition by our a priori inferiority margin of 2%. The effect estimates will reveal clinical non-inferiority of the Get Social condition if the confidence interval lies completely above $-\Delta$ or clinical non-inferiority of the traditional condition if the confidence interval lies completely below $+\Delta$, i.e., 2%.

Secondary non-inferiority outcomes

Secondary non-inferiority outcomes (dietary intake and physical activity at 12 months) will be examined using the same approach as described for the primary outcome. Linear multivariable models will be used to estimate change in daily caloric intake at 12 months; such models are reasonable given the target sample size and that changes in these outcomes are approximately normally distributed. We anticipate using log transformation to estimate change in physical activity variables, given that physical activity data tends to be skewed. The distribution of secondary outcomes will be explored graphically and inform the primary outcome analysis; analyses will be modified as needed through transformation of the data.

Cost

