Linear multivariable models will be used to estimate change in daily caloric intake at 12 months; such models are reasonable given the target sample size and that changes in these outcomes are approximately normally distributed. We will examine the proportion of participants engaging in 150+ minutes/week of moderate/vigorous intensity physical activity (MVPA) using generalized estimating equations with a logit link function and incorporating repeated measures over time. For participants missing MVPA at either follow-up timepoint will use a baseline observation carried forward approach to impute their activity level (150+ vs <150 MVPA mins/week) at that timepoint. The distribution of secondary outcomes will be explored graphically and inform the primary outcome analysis; analyses will be modified as needed through transformation of the data.

Cost

We will calculate total intervention delivery costs per participant by treatment condition using time reported by intervention staff and convert to per-participant costs using national salary data from the Bureau of Labor Statistics. We will conduct sensitivity analyses to estimate a range of per-participant costs after varying the inputs (e.g., time spent conducting intervention, different intervention tasks, salary estimates). While we had originally aimed to examine costs for participants to participate in their respective intervention, we discovered methodologic challenges with collecting accurate and complete data from participants. As a result of what we learned, we have launched a separate study to develop methods for accurately collect participant time spent to participate in a social media delivered behavioral intervention. Without participant-level data, we are unable to conduct the analyses originally planned. Instead, we report the total intervention delivery costs per participant in both hours and dollars per participant for each of the two interventions.

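### Baseline calorie intake is collected but is not a prespecified covariate in the 12-month intake analysis, which is therefore less precise than it could be

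*SAP*

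**What the plan says.** For calorie intake, the SAP (Secondary non-inferiority outcomes) states: "Linear multivariable models will be used to estimate change in daily caloric intake at 12 months". It lists no terms for that model.

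The protocol (Data Analysis, Secondary non-inferiority outcomes) says that dietary intake and physical activity at 12 months "will be examined using the same approach as described for the primary outcome". The protocol's primary model is described "with percent weight loss as the dependent variable and study condition as the independent variable"; no other term is named.

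The only covariate rule stands under Preliminary analysis in both documents: "If groups differ on certain characteristics, these variables will be included as covariates in the primary analyses". It gives no criterion for a difference and is worded for the primary analyses.

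Baseline intake is measured. The protocol's baseline visit includes "three 24-hour diet recall interviews, and PCP approval", and the 6- and 12-month visits include "three 24-hour diet recall interviews, and repeated baseline measures". Not completing the baseline measures is an exclusion criterion, so each randomised participant should have the baseline value.

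The protocol's Justification of Sample Size gives 90% power for change in intake "with a non-inferiority margin of 182 kcal/day with SD=500 kcal/day", with 131 evaluable participants per arm and alpha 0.05.

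**The concern.** A change score subtracts the whole baseline value, which amounts to fixing the baseline coefficient at one. Intake averaged over three recall days is a noisy measure, so its correlation with intake a year later is likely to be well below one. Some of the subtracted baseline is then noise. The arm that happens to start higher tends to show a larger fall whatever the treatment does. Regressing on baseline lets the data set the coefficient and removes that noise.

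Non-inferiority is decided by where an interval limit falls, so an avoidably wide interval lowers the chance of a clear answer. If baseline intake enters only when the arms look different, most of the gain is lost, and the choice of model is made after seeing the data.

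**Working it through.** **Inputs from the protocol:** margin 182 kcal/day, SD 500 kcal/day (read as the SD of the change), 131 per arm, alpha 0.05, 90% power, true difference zero.

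**Assumptions not in the documents:** equal variances at baseline and 12 months, and a baseline to 12-month correlation r of 0.3 to 0.7.

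**1. Reproduce the plan's figure.** The standard error of the unadjusted difference in change is 500 × sqrt(2/131) = 61.8 kcal/day. At one-sided 0.05 the margin for 90% power is (1.645 + 1.282) × 61.8 = 181 kcal/day, against 182 stated. Power at 182 is 90.2%. The protocol does not state the sidedness. One-sided 0.025 would give a margin of about 200, so the stated figure corresponds to one-sided 0.05.

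**2. Compare the two models.** Let s be the SD of intake at each visit.

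- Change score: variance 2(1 − r)s².
- Adjusted for baseline: variance (1 − r²)s².
- Ratio of standard errors, adjusted to unadjusted: sqrt((1 + r)/2).

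| Model | SE ratio | SD (kcal/day) | Margin at 90% power | Power at 182 | n per arm for 90% power at 182 |
|---|---|---|---|---|---|
| Change score | 1 | 500 | 181 | 90.2% | 130 |
| Adjusted, r = 0.3 | 0.81 | 403 | 146 | 97.7% | 85 |
| Adjusted, r = 0.5 | 0.87 | 433 | 157 | 96.0% | 97 |
| Adjusted, r = 0.7 | 0.92 | 461 | 167 | 93.9% | 110 |

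To match the adjusted precision, an unadjusted analysis would need 131/0.65 = 202 per arm at r = 0.3, or 131/0.85 = 154 at r = 0.7.

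**3. Where the extra variance comes from.** The identity 2(1 − r) = (1 − r²) + (1 − r)² splits the change-score variance into the adjusted variance and a part due to chance baseline differences. A baseline difference D between arms moves the unadjusted contrast by −(1 − r)D. At r = 0.5 the baseline SD is 500/sqrt(2 × 0.5) = 500, so one standard error of the baseline difference is 61.8 kcal/day and the shift is 0.5 × 61.8 = 30.9. The adjusted standard error is 433 × sqrt(2/131) = 53.5, and 53.5² + 30.9² = 3,817, which matches 61.8² = 3,819 within rounding. The imbalance shift and the wider interval are therefore the same quantity.

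**4. Check by simulation** (20,000 trials for each r, 131 per arm, normal data). The third column adjusts only when baseline intake differs at p < 0.05, an assumed reading of the covariate rule.

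| r | Power, change score | Power, always adjusted | Power, adjusted only if p < 0.05 |
|---|---|---|---|
| 0.3 | 90.3% | 97.8% | 91.5% |
| 0.5 | 90.5% | 95.9% | 91.4% |
| 0.7 | 90.2% | 93.6% | 90.6% |

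Mean estimates were within 1 kcal/day of the true value throughout. Type I error at the margin was 4.8% to 5.2% for both the change score and standing adjustment.

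**The case against.** **The SAP may already intend it.** The word multivariable implies terms beyond condition, and a model of change on condition plus baseline fits the sentence. This stands: a reader might infer that the SAP rules out baseline intake, and it does not. The gap is that the term is not named.

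**The imbalance rule may cover it.** Because the protocol ties dietary intake to the primary approach, the rule can be read as reaching this outcome. That reading is fair, but the rule has no criterion, and under the reading simulated above it recovers little of the power.

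**The planned test is sound.** This also stands. A reader might infer bias, or count chance imbalance as a second harm beside the wider interval. Under randomisation the change score is unbiased on average and its type I error holds, and step 3 shows that the imbalance effect is already inside the unadjusted standard error.

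**The stake is modest.** The outcome is secondary. The protocol derived the 182 kcal/day margin from the sample size and SD so as to give 90% power, so the plan meets its design power by construction. Expressing a shift as a share of that margin says nothing about clinical consequence.

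**The size rests on an assumed correlation.** True. The gain shrinks as r rises: at r = 0.8 adjusted power is about 93%. The direction is the same for any r below one.

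**Conclusion.** The point holds as an efficiency gap in a secondary analysis. Baseline intake is not a standing covariate in either document, although it is collected before randomisation. Adding it would cut the standard error by 19% (r = 0.3) to 8% (r = 0.7) and raise power at 182 kcal/day from about 90% to about 98% and 94% respectively. These figures assume equal variances, a change SD of 500, 131 per arm and one-sided 0.05. The direction is secure; the size depends on a correlation that the documents do not give.

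A reader might extend the point to the SAP's physical activity model, fitted "using generalized estimating equations with a logit link function and incorporating repeated measures over time". The documents do not support that. Baseline activity may already be one of the repeated measures, and missing follow-up activity is filled with the baseline status, so for those participants the outcome would equal a baseline covariate by construction. No change to that model follows from this point.

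Weight: free improvement, low to moderate severity.

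**What to change.** In the SAP, under Secondary non-inferiority outcomes, state that 12-month intake (or change in intake) is regressed on study condition and baseline mean kcal/day, averaged over the baseline recalls, in every case and regardless of observed imbalance. State that the condition coefficient and its interval are judged against the protocol's 182 kcal/day margin. With baseline in the model, the condition coefficient is the same whether the outcome is 12-month intake or change, and it stays in kcal/day.

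The cost is one sentence and one degree of freedom. No new data, larger sample or change of margin is needed.
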